Appendix E: Opt-in Letter & Opt-out letter74

The VA Diabetes Trial Follow-up Study (VADT-FS)

PREFACE

CSP #465, “Glycemic Control and Complications in Diabetes Mellitus Type 2,” was a randomized unblinded clinical trial comparing tight glycemic control to standard glycemic control and was conducted at 20 VA medical centers. One thousand seven hundred and ninety one patients were randomized over the 2 ½ year accrual periods and then followed for an additional 5 years. Follow-up averaged between 5 and 7 years depending upon when the patient was enrolled in the study. Patients were seen on average every three months in the VA Outpatient Clinics. Hypertension and hyperlipidemia were aggressively treated in patients in both treatment arms. Education regarding diet, exercise, smoking cessation and management of hyper and hypo-glycemic reactions was also provided. Data were collected throughout the study on the patients’ physical status, adverse and serious adverse events, concomitant medications, and study end points including mortality. The study was conducted under an FDA IND and consisted of broad use of all anti-diabetic treatments commercially available between 2000 and 2008 including oral medications and insulin. Study required medications and all study clinic visits were provided free of the usual VA co-pay. Active clinical follow-up of the sample ended on May 31, 2008. With the end of the clinical trial the patients were transitioned back to usual patient care services.

It is important to clarify that with the completion of the active clinical trial and transitioning of patients to this observational trial, all responsibility for the care, treatment and oversight of the study patients became the responsibility of the patients’ Primary Care Physician. The VA Diabetes Trial Follow-up Study (VADT-FS) is not collecting adverse or serious adverse events, is not required to file FDA reports or actively treat or have any “hands-on” care responsibility for the study participants.

The ongoing VADT-FS consists of centralized computer database searches and annual survey questionnaires related to quality of life and self-reported events pertinent to the CSP #465 study.

The VADT-FS is very limited in scope compared to the clinical trial and is restricted to the activities stipulated in the proposal contained on the following pages.

VADT Follow-up Study (VADT-FS)

Abstract:

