Currently employed	735 (41%)
College graduate	367 (20%)
Previous macrovascular event	724 (40.4%)
Current cigarette smoker	257 (14%)
Hypertension	1293 (72%)
Diabetic neuropathy	761 (43%)
BMI (kg/m ²)	31 ±4
A1c(%)	9.4±1.4%
Systolic BP (mmHg)	132 ± 17
Diastolic BP (mmHg)	76 ± 10
Total cholesterol (mg/dL)	183 ± 47
LDL cholesterol (mg/dL)	108 ± 32
HDL cholesterol (mg/dL)	36± 10
Triglycerides (mg/dL)	212 ± 275

The intervention and control subjects were similar in major demographic characteristics, baseline metabolic control and in key CV risk factors, suggesting that randomization was successfully achieved.

VADT Protocol and Subject Follow-up:

Detailed information on the VADT protocol can be found in the main manuscript published in January, 2009, in the New England Journal of Medicine (Abraria et al., 2009), however, here we include some background and key aspects relevant to the VADT-FS. The VADT was designed to do the best job possible of isolating the effects of hyperglycemia in patients with type 2 diabetes. In order for the study to address different levels of glycemic control, and minimize potential medication specific effects, the protocol strove for both treatment groups to receive near-equal distribution of therapeutic classes (insulin segretagogues and sensitizers, exogenous insulin) with ultimately, the main difference between treatments arms expected to be related to the dose of insulin. In addition, the VADT protocol tried to achieve optimal management of all other CV risk factors in both intervention and control patients to answer the question, “What is the incremental benefit of intensive glycemic control once blood pressure, lipids and other CV treatments are optimized.

The success of the VADT protocol in achieving the above goals has been impressive and is a tribute to the hard work and dedication of the VADT site investigators, and especially, the nurse coordinators. The VADT achieved and has maintained substantial A1c separation since year 1 1/2 of the trial (averaging a 1.5 point A1c median separation, with the A1c being 6.9in the intensive arm and 8.4% in the standard treatment arm.

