(6) *Severe Visual Impairment*: defined as poor or worse visual function on the general visual function question on the National Eye Institute Visual Function Questionnaire.(Mangione, 2001; Naeim, 2006; Raphael, 2006)

(7) *Other major procedures/diagnoses*: categorized as, a) photocoagulation or vitrectomy, b) amputation.

(8) *Self-reported health status*: diabetes-related quality of life, using an instrument adapted for type 2 DM patients from the DCCT ([name], 1998; Saudek 1996). This survey tool has been used since the inception of the VADT and will be continued in the annual survey.

* $GFR (mL/min/1.73 m^2) = 175 \times (Cr)^{-1.154} \times (Age)^{-0.203} \times (0.742 \text{ if female}) \times (1.212 \text{ if African American})$

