Although eye disease is not a component of the VADT-FS's primary outcome, it is a very important component of a secondary outcome (major microvascular events). As above, the discontinuation of standard routine physical examinations makes continuation of visual acuity and retinopathy stage determinations problematic. Fortunately, there is now available a patient self-report visual function tool that has been developed with NIH support. (Mangione, 2001; Naeim, 2006; Raphael, 2006) This National Eye Institute Visual Function Questionnaire includes a validated single question for general visual function, and those reporting poor or worse function on this item have been validated to have substantial functional impairment impacting their quality of life (Mangione, 2001 and personal communication with [name] in January 2007). Although caution is always advised when including a new measure during the course of a longitudinal study, we feel that the adoption of this validated item measuring marked visual impairment is preferable to dropping measures of visual function altogether. Patients with reported visual problems will be informed that they can complete their surveys either using the assistance of their designated surrogate or by telephone, whichever they prefer.

Primary study end-point:

Major CV events (non-fatal MI resulting in hospitalization, non-fatal stroke, new CHF, amputation for ischemic diabetic gangrene, or CV-related death).

The proposed primary end-point of the VADT-FS is slightly more restrictive than the primary end-point of the VADT [excluding some CV procedures and subclinical AMI's based upon ECG changes alone] because the increased statistical power of the VADT-FS will allow greater focus on major clinical outcomes and avoid outcomes that are more difficult to discern (e.g., worsening of symptoms) or are more discretionary (e.g., cardiac

procedures).

Major secondary end-points:

1. CV mortality
2. Major microvascular complications (end-stage renal disease, or amputation for non-traumatic, non-ischemic diabetic gangrene).
3. Health-related quality of life (as measured by the modified DCCT tool on a 0-100 point scale)
4. Total mortality

Update

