original study glycemic treatment arms will be analyzed as per original intent-to treat using methods identical to the current VADT study. Life table methods and the log-rank test will be used to compare complication-free survival between the two treatment groups. (Halpern, 1987) Preliminary analyses suggest that the treatment groups were quite similar on important factors at baseline, so we do not anticipate needing to use Cox proportional hazards regression to control for baseline confounding. (Halpern, 1987) However, Cox proportional hazards regression methods will be used to perform a time-dependent covariate survival analysis of the primary outcome. This analysis will adjust for risk factors post intervention such as A1 c, weight, BMI, SPB, DBP, cholesterol, HDL, LDL, use as time dependent covariates. The progress report will include these post-intervention risk factors summarized over time as available through database search.

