Objective #2. To determine the long term effects of intensive glycemic control in type 2 diabetes on four secondary outcomes: a) cardiovascular mortality, b) major microvascular complications, c) health-related quality of life, d) total mortality, and e) major microvascular or macrovascular (end-stage renal disease, amputation for either ischemic or non-ischemic gangrene, CV-related death, or nonfatal MI, stroke, or new CHF). Statistical analyses for secondary outcomes will be identical to those used for the primary outcome, with the exception of microvascular complications and health related quality of life. Since one of the microvascular complications, severe visual impairment, is from the annual survey, survival analysis is not appropriate for the inaccuracy of the time of the record but logistic regression analysis. Since health related quality of life is a continuous measure, survival analysis will not be appropriate for this secondary outcome. The Student t-test will be used to evaluate for differences in mean quality-of-life scores in the two treatment arms, with use of robust methods if there is evidence that variance estimates vary between the two groups. It is well known that if there is a substantial difference in survival between intervention groups, health related quality of life results can be misleading unless the survival differences are accounted for. Therefore, if there are substantial differences in survival between treatment groups, an alternative analysis accounting for missing data due to mortality is a Bayesian imputation approach. (Revicki, 2001) Again, since substantive differences in baseline attributes did not occur, we do not feel that controlling for potential confounders using ordinary least squares regression is necessary.

Update

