We have added a composite measure “Major Microvascular & Macrovascular Events, which is simply an aggregate of the primary outcome with the secondary outcome for microvascular outcomes. Statistical analyses for secondary outcomes will be identical to those used for the primary outcome, with the exception of health related quality of life. Since health related quality of life is a continuous measure, survival analysis will not be appropriate for this secondary outcome. The Student t-test will be used to evaluate for differences in mean quality-of-life scores in the two treatment arms, with use of robust methods if there is evidence that variance estimates vary between the two groups. It is well known that if there is a substantial difference in survival between intervention groups, health related

quality of life results can be misleading unless the survival differences are accounted for. Therefore, if there are substantial differences in survival between treatment groups, an alternative analysis accounting for missing data due to mortality using a Bayesian imputation approach (Revicki, 2001), which will be done by Ann Arbor according to their IRB permission on mortality data collection on all VADT population except the terminated. Again, since substantive differences in baseline attributes did not occur, we do not feel that controlling for potential confounders using ordinary least squares regression is necessary. For the quality of measure, we will deal with confounding due to systematic mortality differentials between treatment arms by using selection models, as recommended in *Assessing Quality of Life in Clinical Trials: Methods and Practice* (eds. Fayer P, Hays R, April 2005.)

Update: (Early Analysis)

The major protocol amendment for the VADT-F was that a mid-point analysis would be conducted and reported, which was made and published as planned. We now plan for an early analysis to take place shortly before data is fully completed with adjudicated outcomes and locked. There is to prepare to submit an important presentation in time to take place at the American Diabetes Association (ADA) 2018 which is planned to be made in conjunction with publication of the corresponding manuscript. Below we provide the full justification for this analysis.

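### Baseline balance is the only reason given for leaving quality of life unadjusted; it answers confounding, not precision, and an earlier score on the same tool may be going unused

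*Combined protocol and SAP*

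**What the plan says.** Quality of life is a major secondary end-point: "Health-related quality of life (as measured by the modified DCCT tool on a 0-100 point scale" (Major secondary end-points). Under Analysis Plan, Objective #2, and again in its Update, the method is: "The Student t-test will be used to evaluate for differences in mean quality-of-life scores in the two treatment arms". Robust methods are added if the variances differ. If survival differs substantially between arms, a Bayesian imputation is offered, and the Update adds selection models. None of these is said to use an earlier quality-of-life score.

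Regression is declined on one ground: "since substantive differences in baseline attributes did not occur, we do not feel that controlling for potential confounders using ordinary least squares regression is necessary". The supporting statement, after Table 1, reads "The intervention and control subjects were similar in major demographic characteristics, baseline metabolic control and in key CV risk factors". Quality of life is not in that list.

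On the instrument, Measuring Endpoints, item (8), says: "This survey tool has been used since the inception of the VADT and will be continued in the annual survey". The section on the Cooperative Studies Program Coordinating Center describes the first follow-up survey, in June 2009, as the baseline for quality of life. The Missing Data section restricts the quality-of-life analysis to survey respondents.

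**The concern.** Covariate adjustment in a randomised comparison has two separate uses. One is to remove chance imbalance, and observed balance is a fair reply to that. The other is to remove outcome variation that a pre-randomisation measure explains, which narrows the interval whether or not the arms are balanced. The plan considers only the first. For a questionnaire score, the natural covariate is the same person's score before randomisation.

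If such a score is held, the comparison uses less information than the trial has. The plan gives no numerical power for this outcome; Statistical power says only that it will be better than for the event outcomes.

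There is also a trap. An analyst who decides to adjust could take the June 2009 survey at its label. That survey followed the intervention, so conditioning on it could remove part of the treatment effect.

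**Working it through.** There is no quality-of-life power figure in the plan to reproduce.

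**1. When the June 2009 survey falls.** The Preface describes two and a half years of accrual ("accrual periods and then followed for an additional 5 years") and says "Active clinical follow-up of the sample ended on May 31, 2008". Five years before 31 May 2008 is about May 2003, when accrual ended. Two and a half years before that is about December 2000. June 2009 is therefore about 6.0 to 8.5 years after randomisation and one year after active follow-up ended. The plan does not name the survey year for the t-test, and a later survey lengthens the gap.

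**2. Inputs.**
- Main Cohort: 1,031 (Statistical power, Update). Response in 2011: 82.7% (Self Report, Updates). 1,031 x 0.827 = 853, an upper bound because later deaths and drop-out reduce it. I also show an assumed 600.
- Two-sided alpha 0.05 (notes to Table 2).
- Assumed, because the documents do not give them: 1:1 allocation among respondents, a true difference of 0.2 SD, and the correlation r between the pre-randomisation and follow-up scores. Over six years or more, r of 0.2-0.3 seems more plausible than 0.5-0.6.

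**3. Formulas.** For N respondents in two equal groups, the SE of the difference in SD units is sqrt(4/N) for the t-test and sqrt(4(1 - r^2)/N) for ANCOVA. Power comes from the noncentral t distribution.

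**4. Results at 0.2 SD.** For N = 853 the t-test SE is sqrt(4/853) = 0.068.

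| Analysis | Variance factor | Power, N = 853 | Power, N = 600 |
|---|---|---|---|
| t-test | 1.00 | 83.1% | 68.6% |
| ANCOVA, r = 0.1 | 0.99 | 83.4% | 69.1% |
| ANCOVA, r = 0.2 | 0.96 | 84.6% | 70.4% |
| ANCOVA, r = 0.3 | 0.91 | 86.4% | 72.7% |
| ANCOVA, r = 0.5 | 0.75 | 92.1% | 80.6% |
| ANCOVA, r = 0.6 | 0.64 | 95.4% | 86.4% |

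At r = 0.2-0.3 the gain is 1.5 to 3.3 points with 853 respondents and 1.8 to 4.1 with 600.

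**5. Missing earlier scores.** If a share m of respondents lack the score and are dropped, the effective size is N(1 - m)/(1 - r^2). This falls below N once m exceeds r^2: 4% at r = 0.2 (34 of 853) and 9% at r = 0.3 (77 of 853). If everyone is kept, with the overall mean plus a missing indicator, the variance factor is 1 - (1 - m)r^2. For N = 853 and m = 10%:
- complete-case ANCOVA: 80.6% (r = 0.2) and 82.7% (r = 0.3), both below the t-test's 83.1%;
- mean plus indicator: 84.4% and 86.1%.

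So, in the plausible range of r, how missing earlier scores are handled decides whether adjustment gains anything.

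**The case against.** **It is a small efficiency preference on one of five secondary outcomes.** Largely true. The effect size and r are assumed, and at r = 0.1 the gain is about 0.4 points. What stands is that the cost is low and that the plan's stated reason does not bear on precision.

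**The earlier score may not be usable.** Also true. Use of the tool since the start of the VADT makes a pre-randomisation score likely, but no section says when it was first given or how complete it is. The proposal is therefore conditional on a data check.

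**Selection is the larger risk.** Fair. The analysis set is consenting, surviving respondents; 853 is 48% of the 1,791 randomised. A reader might infer either that randomisation fully protects the t-test here or that ANCOVA would repair the selection. Neither follows. Randomisation protects the full cohort, not this subset, and adjusting for an earlier score does not remove selection through death or non-response. The plan has imputation and selection models for mortality differences, and they should stay. For the same reason, the mean-plus-indicator device loses its full guarantee among respondents.

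**Does the argument extend to the primary outcome?** Objective #1 gives similar reasoning: "so we do not anticipate needing to use Cox proportional hazards regression to control for baseline confounding". A reader might infer that the log-rank test needs replacing. The documents do not support that. The plan chooses it for continuity with the VADT intent-to-treat analysis, and any gain from adjustment would rest on a prognostic strength that the documents do not give.

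**Could the time-dependent Cox model be taken for an adjusted treatment effect?** Objective #1 already gives the intent-to-treat comparison to the log-rank test and describes the Cox covariates as arising after the intervention. Calling that model observational, as the section on mechanisms of action does for similar analyses, is an optional wording point.

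**Conclusion.** The point holds as a modest precision issue for one secondary outcome. Balance at baseline is not a reason to leave a prognostic pre-randomisation score out, and the plan's balance statement does not cover quality of life. The expected gain is about 1.5 to 4 power points at r = 0.2-0.3, close to nothing at r = 0.1, and large (9 to 12 points with 853 respondents) only if r is 0.5-0.6. These figures rest on an assumed 0.2 SD difference, equal arms among respondents, a complete earlier score and assumed values of r. The point does not show that the t-test is biased by omitting the score, and it gives no reason to change the primary analysis.

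**What to change.** 1. The sponsor confirms that a pre-randomisation score on this tool exists, how complete it is among respondents, and that it can be joined through the ID cross-link held at the Hines coordinating center (Data Collection Sources).
2. If so, specify ANCOVA on that score with robust standard errors, in the same respondents and survey year or years as the t-test; the year must be named. Report the planned t-test beside it. State that the June 2009 survey is not the covariate.
3. Keep respondents who lack the earlier score, using the overall mean plus a missing indicator, or multiple imputation. The plan's covariate imputation currently covers only the interaction and mechanism analyses, so the rule must be written with the new covariate. Check that missingness of the earlier score is similar by arm among respondents.
4. Fix all this without access to quality-of-life results by arm. The Data Monitoring Committee sees unblinded secondary endpoints every year and the Hines statisticians compile the reports. The Executive Committee decides protocol changes and does not see those reports. Mid-point results are published, and the documents do not say whether quality of life was among them. If those deciding already know results by arm, the t-test leads and ANCOVA is supporting.
5. Keep the imputation and selection models for mortality.

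The cost is a data check and a short SAP amendment, with no new data collection if the score is held.
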